2.3.2 Benefit Assessment

Regorafenib is a potent MKI with an extensive kinase-inhibition profile, exhibiting robust efficacy data in pre-treated HCC patients. The RESORCE study showed similar clinical benefit for regorafenib for the second line setting as observed with sorafenib in the first line. This observed level of clinical benefit in a pre-treated population suggests that regorafenib

Page 34 of 141

has the potential to offer benefit in a patient population previously treated with other 1L systemic therapy, justifying studying it in the 2L setting.

Recently published data support the combination of an MKI with an anti-PD-L1 as an option for treatment-refractory cancer such as metastatic RCC after progression with a PD-1/PD-L1 immune checkpoint inhibitor. In the Phase 2 trial of lenvatinib in combination with pembrolizumab for disease progression after PD-1/PD-L1 immune checkpoint inhibitor in metastatic RCC, 65% of patients had prior PD-1/VEGF combination therapy and 37% had prior ipilimumab/nivolumab during a median prior duration of immunotherapy of 7 months. The objective response of the study treatment combination was of 51%, with a median PFS of 11.7 months and median DOR of 9.9 months (Lee et al. 2020).

Immune checkpoint inhibitors have shown promising clinical activity and durable responses in patients with HCC. Based on complementary modes of action between MKIs and PD-1 inhibitors and their potentially synergistic effects on the cancer-immunity pathway, the combination of regorafenib and pembrolizumab might provide a greater clinical benefit in HCC patients.

Preliminary data from the Phase 1b study 19497 of regorafenib in combination with pembrolizumab in patients with advanced HCC with no prior systemic therapy have demonstrated a potential efficacy signal in 1L and a tolerable safety profile. As of NOV 2020, 9 out of the 31 participants who started 120 mg regorafenib QD (3 weeks on / 1 week off) and pembrolizumab 200mg Q3W and were evaluable for efficacy achieved PR per RECIST 1.1, with a DCR of 94%. Of the 21 patients who started 80 mg regorafenib QD (3 weeks on / 1 week off) and pembrolizumab 200mg Q3W and were evaluable for efficacy, 3 achieved PR per RECIST 1.1, with a DCR of 86%. Efficacy data for the 80 mg cohort were immature as of the cut-off date for this analysis.

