- At the time of first detection of HCV RNA, send a specimen for HCV genotyping or serotyping (if genotyping is not available) (local laboratory)
- Measure AST, ALT, ALP, Tbil, Dbil, and INR weekly
- Measure HCV RNA levels every 2 weeks
- Therapy with HCV antiviral treatments should be strongly considered.

HCV Flare (hepatitis C exacerbation in participants with HCV RNA positive):

 At the time of first detection of HCV RNA, send a specimen for HCV genotyping or serotyping (if genotyping is not available) (local laboratory)

Page 69 of 141

Table 6–6: Guidance on Assessment and Further Dosing Following Occurrence of Hepatic Events of Clinical Interest

- Measure AST, ALT, ALP, Tbil, Dbil, INR weekly
- Measure HCV RNA levels every 2 weeks
- Therapy with HCV antiviral treatments should be strongly considered

Further information concerning Immune-related hepatitis

Description: Immune-related hepatitis due to study treatment should be suspected if any of the following is seen:

- ALT baseline values are less than 2 × ULN, and AST or ALT laboratory values increase to ≥5 × ULN
- Among participants with baseline ALT ≥2 × ULN, levels increase to >3× the baseline level
- ALT >500 U/L regardless of baseline level
- Total bilirubin >3.0 mg/dL regardless of baseline level

Immune-related hepatitis is a diagnosis made after excluding other possible etiologies for the change. Viral flare (if applicable), biliary or vascular obstruction, infection, medications, and alcohol use must be ruled out (see below).

Management:

- Interrupt pembrolizumab intervention for up to 12 weeks
- Start IV corticosteroid (60 mg/day of prednisone or equivalent) followed by oral corticosteroid
 - Monitor with biweekly laboratory tests including AST, ALT, Tbil, Dbil, ALP, and INR
 - Restart pembrolizumab intervention only if:
 - Abnormal laboratory values resolve to Grade ≤1 or baseline (if abnormal at baseline)
 - Taper steroid over 28 days
 - Steroid treatment is tapered to prednisone <10 mg/day or equivalent
 - Permanently Discontinue pembrolizumab intervention if:
 - Laboratory abnormalities do not resolve within 3 weeks
 - Steroids cannot be lowered to ≤10 mg/day (or prednisone equivalent) within 12 weeks
 - o Evidence of decompensation to CP C status

Further information concerning other causes:

- Rule out infection with blood, urine and ascites culture antibiotics should be started if infection is found

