Event	Regorafenib	Pembrolizumab	
Specific guidance for IMMUNE-	RELATED ADVERSE EVENTS		
General instructions concerning	g pembrolizumab:		
	1. Severe and life-threatening irAEs should be treated with IV corticosteroids followed by oral steroids. Other immunosuppressive treatment should		
begin if the irAEs are not	controlled by corticosteroids.		
Pembrolizumab must be j	permanently discontinued if the irAE does not resolve or the cort	ticosteroid dose is not ≤10 mg/day within 12 weeks of the	
last pembrolizumab treatr	ment.		
The corticosteroid taper s	hould begin when the irAE is ≤ Grade 1 and continue at least 4	weeks.	
4. If pembrolizumab has bee	en withheld, pembrolizumab may resume after the irAE decrease	ed to ≤ Grade 1 after corticosteroid taper.	
Pneumonitis	 G2 or higher: Interrupt until ≤ G1 	G2: Withhold	
 Monitor participants for 	 Restart at same dose level for G2 and decrease by 	Recurrent G2, G3, or G4: Permanently discontinue	
signs and symptoms of	1 dose level for G3/4 ^a	Administer corticosteroids (initial dose of 1-2 mg/kg	
pneumonitis		prednisone or equivalent) followed by taper: add	
 Evaluate participants with 		prophylactic antibiotics for opportunistic infections	
suspected pneumonitis with			
radiographic imaging and			
initiate corticosteroid			
treatment			

Table 6–7: Dose Modification Guidance, Other Immune-related Adverse Events

Event	Regorafenib	Pembrolizumab
Specific guidance for IMMUNE	-RELATED ADVERSE EVENTS	
New onset Type 1 Diabetes Mellitus (T1DM) or G3 or G4 hyperglycemia associated with evidence of β-cell failure • Monitor participants for hyperglycemia or other signs and symptoms of diabetes	• Interrupt until ≤ G1. Restart at same dose level.	 Withhold^b Initiate insulin replacement therapy for participants with T1DM Administer anti-hyperglycemic in participants with hyperglycemia
 Hypophysitis Monitor for signs and symptoms of hypophysitis (including hypopituitarism and adrenal insufficiency) 	• Interrupt until ≤ G1. Restart at same dose level.	 G2: Withhold G3/4: Withhold or discontinue (at the investigator's discretion)^b Administer corticosteroids and initiate hormonal replacements as clinically indicated
Monitor for signs and symptoms of thyroid disorders	 G2: No modifications G3/4: Interrupt until ≤ G2. Restart at same dose level. 	 G2: Continue G3/4: Withhold or discontinue (at the investigator's discretion)^b Treat with non-selective beta-blockers (e.g. propranolol) or thionamides as appropriate

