7.1.1.3 Withdrawal of Pembrolizumab only

Participants MAY be withdrawn from pembrolizumab for the following reasons:

• Participants who experience a delay of more than 12 weeks to receive the subsequent pembrolizumab infusion due to treatment-related toxicity or corticosteroids cannot be

Page 78 of 141

reduced to \leq 10 mg prednisone or equivalent per day within 12 weeks, according to dose modification guidance in Section 6.6.

- Unacceptable toxicity, i.e. event requiring permanent discontinuation of pembrolizumab according to dose modification guidance in Section 6.6.
- Discontinuation of pembrolizumab may be considered for participants who have attained a confirmed CR that have been received at least 8 infusions (24 weeks) of pembrolizumab and had at least 2 infusions with pembrolizumab beyond the date when the initial CR was declared.

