10.2 Appendix 2: Clinical Laboratory Tests

All laboratory analyses detailed in the SoA (Section 1.3.1) and in Table 10–2 and Table 10–3 will be performed locally.

Protocol-specific requirements for inclusion or exclusion of participants are detailed in Section 5 of the protocol. Additional tests may be performed at any time during the study as determined necessary by the investigator or required by local regulations.

AFP will be assessed as described in the SoA (Section 1.3.1).

Serum or urine pregnancy tests are performed as outlined in the SoA (Section 1.3.1). The frequency of pregnancy tests may be higher if required by local regulations. Refer to Section 5.1 for screening pregnancy criteria. Details on Contraceptive Guidance and Collection of Pregnancy Information can be found in Section 10.4.

The schedule for testing and the laboratory tests included in Panel A and B are described in Table 10–1 and Table 10–2, respectively. The schedule and criteria for hepatitis virus testing is outlined in Table 10–3.

Investigators must document their review of each laboratory safety report.

Panel A Panel B Visit (see Table 10-2) (see Table 10-2) Screening (within 7 days of first study intervention) Χa Before each pembrolizumab infusion Χb Before each regorafenib dose after 7 days break Χc Regorafenib D1 for in-between weeks within the first Χ 8 weeks (first 2 cycles) EoT visit Χ Safety follow-up visit Χ

Table 10-1: Laboratory Testing Standard Schedule

D1 = Day 1; EoT = end of treatment; W1D1 = Week 1 Day 1

a: If for any reason tests were performed more than 7 days prior to the first dose of study intervention, they should be repeated on W1D1.

b: If there is a pembrolizumab dosing delay or pembrolizumab withdrawal, Panel A is required at least every 4 weeks on Day 1 before each regorafenib administration

c: Not required if sampling for Panel A has been done within the previous 5 days.

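### Section 7.1.1.3 equates 8 pembrolizumab infusions with 24 weeks, but on this trial's 6-weekly schedule 24 weeks is 4 infusions and 8 infusions cover 48 weeks

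*Protocol*

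**What the plan says.** **The threshold.** Protocol Section 7.1.1.3 lists reasons for which a participant may be withdrawn from pembrolizumab alone. The last entry covers confirmed CR. Stopping may be considered if the participant has had "at least 8 infusions (24 weeks) of pembrolizumab" and at least two further infusions after the date on which CR was first declared.

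**The schedule.** Sections 4.1.1.2 and 6 and Table 6-1 give one regimen, 400 mg every 6 weeks (Q6W). Table 1-1 places infusions at W1, W7, W13 and W19, then every 6 weeks. The Synopsis puts 18 infusions at about 2 years. Section 2.3.2 describes the Phase 1b study of the same combination as using "pembrolizumab 200mg Q3W".

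**Neighbouring 12-week limits.** For immune-related hepatitis, Table 6-6 calls for permanent discontinuation if "Steroids cannot be lowered to ≤10 mg/day (or prednisone equivalent) within 12 weeks", with no start date. Table 6-7, on other immune-related events, calls for it when the corticosteroid "dose is not ≤10 mg/day within 12 weeks of the" last pembrolizumab treatment. The first entry of the 7.1.1.3 list repeats the limit ("10 mg prednisone or equivalent per day within 12 weeks") and refers back to Section 6.6.

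**The concern.** The CR rule joins a count and a duration as if they were the same quantity. On the trial's only schedule they are not. A site that goes by the count waits until W43. A site that goes by the weeks could stop after 24 weeks, with 4 infusions given. Nothing in 7.1.1.3 says which half governs.

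What is at stake is how long participants with CR stay on pembrolizumab, and whether sites treat like cases alike. This is an operative treatment rule, not background text, so it should give one answer.

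**Working it through.** **Inputs.** Threshold of 8 infusions and 24 weeks (7.1.1.3); interval of 6 weeks (Section 6, Table 6-1); first infusion at W1 (Table 1-1); Phase 1b interval of 3 weeks (2.3.2); 18 infusions in about 2 years (Synopsis).

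**1. Reproduce the protocol's equation.** Duration = infusions × interval. With 3 weeks, 8 × 3 = 24 weeks. The printed pair holds only at this interval.

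**2. Repeat it for this trial.** With 6 weeks, 8 × 6 = 48 weeks. The n-th infusion is given at week 1 + 6(n − 1), so the eighth is at 1 + 42 = W43. In the other direction, 24 / 6 = 4 infusions (W1, W7, W13, W19); the fifth is due at W25, just after 24 full weeks. The mismatch is 8/4 = 48/24 = 2.

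**3. Check another count in the protocol.** 18 × 6 = 108 weeks, or 108/52 = 2.1 years, which agrees with the Synopsis. At 3 weeks it would be 54 weeks, about 1 year. The 18-infusion limit is therefore counted correctly on Q6W.

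**4. When the two halves give different answers.** The second condition, two infusions after CR is first declared, also delays stopping. If CR is declared after infusion k and before infusion k + 1, that condition is met at k + 2 infusions. The earliest stop is then max(4, k + 2) infusions on the 24-week half and max(8, k + 2) on the 8-infusion half. This assumes dosing on schedule and confirmation of CR by then.

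| CR declared | k | 24-week half | 8-infusion half | Difference |
|---|---|---|---|---|
| W1 to W7 | 1 | 4 | 8 | 4 infusions (24 weeks) |
| W7 to W13 | 2 | 4 | 8 | 4 infusions (24 weeks) |
| W13 to W19 | 3 | 5 | 8 | 3 infusions (18 weeks) |
| W19 to W25 | 4 | 6 | 8 | 2 infusions (12 weeks) |
| W25 to W31 | 5 | 7 | 8 | 1 infusion (6 weeks) |
| from W31 | 6 or more | k + 2 | k + 2 | none |

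The choice matters only when CR is first declared before the sixth infusion at W31. It then shifts the earliest stop by 1 to 4 infusions.

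**The case against.** The best defence is that the count is the criterion and the weeks are only a gloss. Eight infusions on Q6W always take longer than 24 weeks, so a site that waits for the eighth satisfies both halves. The rule is also permissive: stopping may be considered, nobody is obliged to stop, and few participants may ever qualify. The Phase 1b responses reported in Section 2.3.2 are all partial. All of this limits the consequence. It does not make the sentence right, and the protocol does not say that the count takes precedence. The sponsor may equally have meant 24 weeks.

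A reader might go further and infer that time limits in this part of the protocol were carried over from a 3-weekly schedule without checking, so that the undated 12-week steroid limit in Table 6-6 is a defect of the same kind. The documents do not support that:

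- The 18-infusion limit is counted correctly on Q6W (step 3).
- Table 6-7 is titled for other immune-related events, so its dated rule does not directly contradict Table 6-6. Tables 6-3 and 6-4 already count their 12 weeks from the last infusion.
- Table 6-6 discontinues pembrolizumab if "Laboratory abnormalities do not resolve within 3 weeks" and says "Taper steroid over 28 days". If the taper starts at recovery, that is at most 3 + 4 = 7 weeks from the hold. Counting from the hold or from the last infusion then gives different decisions only if the hold comes more than 12 − 7 = 5 weeks after the last infusion. That can happen, since Table 10-1 schedules laboratory tests "Before each pembrolizumab infusion", but it also needs slow recovery. Longer tapers would widen the gap.
- Section 6.6 presents these tables as support for clinical judgement.

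The missing start date is therefore a wording clarification, and the CR threshold is no evidence about it.

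**Conclusion.** Wrong as written. The two halves of the CR threshold differ by a factor of two on the only pembrolizumab schedule in this trial. The earliest permitted stop differs by up to 4 infusions, or 24 weeks of dosing, if CR is first declared before W13. There is no difference if it is declared from W31 on. These figures assume on-schedule Q6W dosing and timely confirmation of CR.

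The effect is confined to participants with confirmed CR, under an optional rule; how many there would be cannot be derived from the documents. A reader might also infer that the error weakens the primary analysis. It does not: the rule applies only after a response has been confirmed, and neither the 20% null rate nor the sample sizes of 93 and 119 use the threshold. Any influence on duration of response through earlier stopping cannot be sized from the documents. That the 24 weeks came from the Phase 1b schedule is plausible, but it is not stated and the conclusion does not need it.

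**What to change.** In Section 7.1.1.3, replace the threshold with one pair that is consistent on Q6W:

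- at least 4 infusions (24 weeks), which keeps the stated duration; or
- at least 8 infusions (48 weeks), which keeps the stated count.

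The sponsor should confirm which was meant. If it is 4, the requirement for two infusions after CR will usually govern: by step 4, the 4-infusion minimum adds anything only when CR is declared before the W7 infusion. If it is 8, participants with early CR stay on pembrolizumab until at least W43.

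The cost is one corrected number, with no new procedure, visit or analysis. The SAP version history records that recruitment stopped early, so the benefit is limited to participants still on pembrolizumab and to any reuse of this text. If the section is opened for correction, the start date of the steroid limit in Table 6-6 could be added as an optional clarification.

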6.6.4 Dose Modification and Toxicity Management of Infusion Reactions Related to Pembrolizumab

Pembrolizumab may cause severe or life-threatening infusion reactions including severe hypersensitivity or anaphylaxis. Signs and symptoms usually develop during or shortly after drug infusion and generally resolve completely within 24 hours of completion of infusion. Dose modification and toxicity management guidelines on pembrolizumab-associated infusion reaction are provided in Table 6–8.

a: If reductions are required resulting in a dose of less than 60 mg QD of regorafenib, then regorafenib will be permanently discontinued.

b: The decision to withhold or permanently discontinue pembrolizumab is at the discretion of the investigator or treating physician. If control achieved or ≤ Grade 2, pembrolizumab may be resumed.

c: Events that require discontinuation include, but are not limited to: Guillain-Barre Syndrome, encephalitis, myelitis, and other clinically important irAEs (eg, vasculitis and sclerosing cholangitis).

Table 6-8: Dose Modification Guidance, Pembrolizumab-associated Infusion Reactions

Event	Regorafenib	Pembrolizumab	Premedication at Subsequent Dosing of Pembrolizumab
Specific guidance f	or PEMBROLIZUMAB-ASSOCIATED INI	USION REACTIONS	
	scitation equipment should be available at nation, refer to CTCAE v 5.0	the bedside and a physician readily available during the	e period of drug administration
G1 Mild reaction; infusion interruption not indicated; intervention not indicated	No modification	Increase monitoring of vital signs as medically indicated until the participant is deemed medically stable in the opinion of the investigator.	None
G2 Requires therapy or infusion interruption but responds promptly to symptomatic treatment (e.g., antihistamines, NSAIDs, narcotics, IV fluids); prophylactic medications indicated for ≤ 24 hours	No modification	 Stop Infusion Additional appropriate medical therapy may include but is not limited to: IV fluids Antihistamines NSAIDs Acetaminophen Narcotics Increase monitoring of vital signs as medically indicated until the participant is deemed medically stable in the opinion of the investigator. If symptoms resolve within 1 hour of stopping drug infusion, the infusion may be restarted at 50% of the original infusion rate (e.g. from 100 mL/hour to 50 mL/hour). Otherwise dosing will be held until symptoms resolve and the participant should be premedicated for the next scheduled dose. Participants who develop G2 toxicity despite adequate premedication, pembrolizumab 	Participant may be premedicated 1.5h (± 30 minutes) prior to infusion of pembrolizumab with: Diphenhydramine 50 mg p.o. (or equivalent dose of antihistamine). Acetaminophen 500-1000 mg p.o. (or equivalent dose of analgesic).

Table 6-8: Dose Modification Guidance, Pembrolizumab-associated Infusion Reactions

Event	Regorafenib	Pembrolizumab	Premedication at Subsequent Dosing of Pembrolizumab
Specific guidance f	or PEMBROLIZUMAB-ASSOC	NATED INFUSION REACTIONS	
		should be permanently discontinued.	
G3 Prolonged (i.e., not rapidly responsive to symptomatic medication and/or brief interruption of infusion); recurrence of symptoms following initial improvement; hospitalization indicated for other clinical sequelae (e.g., renal impairment, pulmonary infiltrates) G4 Life-threatening; pressor or ventilator support indicated	No modification	Stop Infusion Additional appropriate medical therapy may include but is not limited to: Epinephrine (In cases of anaphylaxis, epinephrine should be used immediately) IV fluids Antihistamines NSAIDs Acetaminophen Narcotics Oxygen Pressors Corticosteroids Increase monitoring of vital signs as medically indicated until the participant is deemed medically stable in the opinion of the investigator. Hospitalization may be indicated. Pembrolizumab should be permanently discontinued. **In cases of anaphylaxis, epinephrine should be used immediately. Participant is permanently discontinued from further study drug treatment	No subsequent dosing
Appropriate requesits	ation equipment should be avail	able at the bedside and a physician readily available during the	neriod of drug administration. For

Appropriate resuscitation equipment should be available at the bedside and a physician readily available during the period of drug administration. For further information, refer to the Common Terminology Criteria for Adverse Events v5.0 (CTCAE) at http://ctep.cancer.gov

CTCAE = Common Terminology Criteria for Adverse Events; G1/2/3/4 = Grade 1/2/3/4; IV = intravenous; NSAID = nonsteroidal anti-inflammatory drug; p.o. =

CTCAE = Common Terminology Criteria for Adverse Events; G1/2/3/4 = Grade 1/2/3/4; IV = intravenous; NSAID = nonsteroidal anti-inflammatory drug; p.o. = per os (oral)

Page 75 of 141

6.6.5 Rescue Medication and Supportive Care

Participants should receive appropriate supportive care measures as deemed necessary by the treating investigator. Suggested supportive care measures for the management of AEs with potential immunologic etiology are outlined along with the dose modification guidelines in Section 6.6.3 (Table 6–7). Where appropriate, these guidelines include the use of oral or IV treatment with corticosteroids, as well as additional anti-inflammatory agents if symptoms do not improve with administration of corticosteroids. Note that several courses of steroid tapering may be necessary as symptoms may worsen when the steroid dose is decreased. For each disorder, attempts should be made to rule out other causes such as metastatic disease or bacterial or viral infection, which might require additional supportive care. The treatment guidelines are intended to be applied when the investigator determines the events to be related to pembrolizumab.

Note: If after the evaluation of the event it is determined not to be related to pembrolizumab, the investigator does not need to follow the treatment guidance. Refer to Section 6.6 for guidelines regarding dose modification and supportive care.

It may be necessary to perform conditional procedures such as bronchoscopy, endoscopy, or skin photography as part of evaluation of the event.

6.7 Intervention after the End of the Study

Continued Access: Participants who are still on study intervention at the time of study completion/termination may continue to receive study intervention if they are experiencing clinical benefit. Continued access to study intervention will end when a criterion for discontinuation is met or 18 administrations of pembrolizumab had been administered. However, continuation of treatment with regorafenib can be individually discussed with the investigator for participants who do not experience disease progression after 2 years based on clinical benefit.

7. Discontinuation of Study Intervention and Participant Discontinuation / Withdrawal

All participants who enter the study should complete all applicable study periods, including the EoT visit. Participants can be withdrawn from any study period at any time.

Discontinuation from the intervention period alone does not constitute withdrawal from the study.

Participants who withdraw from the intervention period for any reason should come to the site for the safety follow-up visits and are to be encouraged to remain on the study for follow-up of primary, secondary and other objectives (i.e. continue in the active follow-up and long-term follow-up periods). Participants are expected to participate in follow-up unless they explicitly object. Withdrawal of consent to the intervention period should be documented in the participant's medical record. If the participant does not wish to be followed up further, this additional consent withdrawal for follow-up must also be documented.

For a full list of withdrawal criteria, refer to Section 7.2.

In all cases, the reason for withdrawal must be recorded in the participant's medical records and in the eCRF. For participants who withdraw consent, no further study-related procedures will be allowed. The participant will not suffer any disadvantage as a result.

Page 76 of 141

All participants who discontinue due to AEs should be followed up until they recover or stabilize, and the subsequent outcome recorded. If any participant dies during treatment, or within 30 days after the last dose of regorafenib if a participant was on regorafenib monotherapy, or within 90 days after the last dose of regorafenib/pembrolizumab treatment or pembrolizumab monotherapy administration, the investigator or his/her designated associate(s) will inform the sponsor and the cause of death should be recorded in detail within 24 hours of awareness on a SAE form and transmitted to the sponsor.

